## Is Your Infant Eligible For Kangaroo Care (Cont.)

- ❖ The Apgar scale can be used to judge if the infant ready for KC;
- **APGAR score 9 – 10**
  - very healthy & start immediately
- **APGAR score 7 – 8**
  - healthy & probably to start KC within the next 2 days, if not within the first 2 hours of birth.
- **APGAR score 5 – 6**
  - may need to wait 3 to 5 days before beginning KC
- **APGAR 0 – 4**
  - won't be able to start KC for 7 days or more.

### APGAR SCORING

INDICATOR	0	1	2
HR	Absent	<100	>100
RR	Absent	Slow, irregular weak cry	Good vigorous cry
MUSCLE TONE	Flaccid limp	Some flexion of extremities	Good flexion, active motion
REFLEX IRRITABILITY	NR	Weak cry and grimace	Vigorous cry, cough, sneeze
SKIN COLOR	Blue	Acrocyanosis	Pink

24

## Positioning For Safe Kangaroo Care

1. Place **ON** abdomen, allow to crawl to **breast** OR...
2. Place infant an **Upright** **between** the breasts (prepare for breastfeeding)
3. Head should be **midline** turned to side and neck straight (to keep airway open)
4. Arm and legs in **FLEXED POSITION**

(flexion contribution to advanced motor development in KC)

[figure not shown]
[figure not shown]

Figure 4 : Positioning of Kangaroo Mother Care

25

26

## KC Position Neuro-psychology

- In KC, the **C-Afferent nerves** (chest nerves are activated at birth, from **umbilicus** to **sternum** & across infant's back in newborn period and have greatest **DENSITY** here in newborn period) are stimulated.
- (Morrison L et al., 2011, Reduced C-Afferents fibers density affect perceived pleasantness and empathy for touch Brain, 134, 1116-1126)

[figure not shown]
[figure not shown]
21

## Cont.

- **C-Afferent nerves** are exquisitely **sensitive to chest-to-chest, non phasic skin stimulation**.
- (JUVNAS-Moberg., Arn, Magnusson, D. (2005) The physiobiology of emotion: the role of the oxytocinergic system, IJOBM 12(2), 59-65)
- encode it as **Pleasant Touch**
- (Morrison, L et al., 2011) Reduced C-Afferents fibre density effects perceived pleasantness and empathy for touch brain.

22

## Positions The Baby For KC

23

#### POSITION OF THE BABY

- Most love to lie in a prone position, cry less and feels more comfortable
- Relieves abdominal discomfort by passage of flatus and reduce risk of aspiration

Figure 5 : Shows the arms and legs in flexed and prone position.

30

[figure not shown]

Figure 6 : Show the safe and warning for KC positioning

31

Table 2 : Types Of Sleep

Active sleep	Eye closed, irregular respiratory patterns, body movements present.
Quiet sleep	Eyes closed, regular respiratory pattern, no body movements.
Indiscriminant sleep	Chaotic; neither active nor quiet sleep.
An infant's sleep cycle	
A 60 minute cycle that includes:
 
 
5 to 10 minutes of active sleep, accompanied by frequent arousals to awake and crying states.
 
A long period of deep, quiet sleep, hopefully 40 to 50 minutes, with very few minor arousals (fluttering eyes, only lip movements or slight flutter of a finger), so minor the infant returns to deep quite sleep.
 
A return to active sleep for 2 to 5 minutes.
 

32

## CONT.

- Oxygen is regularly used in preterm infants because of their immature lungs and oxygen is important for metabolism and physiological functions
- This study has shown an improvement in peripheral oxygen saturation (SapO2) after 30 min of KMC. Researchers have explained the improvement in oxygenation by the fact that the upright position of KMC increases the efficiency of the diaphragm and pulmonary function
- On other hand, other researchers have concluded no significant changes in oxygen saturation and consumption during KMC

33

## CONT.

- Improvement in CBF has been probably mediated by stabilized cardio respiratory parameters during sleep.
- Another explanation; is that human hairy skin has slow conducting unmyelinated (C) afferents that respond to touch and skin to skin contact during KMC.
- Activation of these fibers stimulates the insular cortex (limbic system) to produce mediators (endorphins, neuropeptide and calcitonin gene-related peptide), which in turn enhance postsynaptic Nitric Oxide Synthase.
- Nitric oxide induces smooth muscle relaxation and plays a pivotal role in regulating blood flow in the microvasculature.

34

## The Benefits of Kangaroo Care

### ❖ Infant:

1. A **stable heart rate**
2. Less **hypoglycemia**, rare **hypothermia** (Boundy et al., 2016)
3. More **regular breathing**
4. Improved dispersion of oxygen throughout the body.
5. Prevention of **cold stress**. (When preemie becomes too cold, he burns up much needed oxygen and calories to stay warm)
6. Longer periods of **sleep** (during which the brain matures)
7. Improves **weight gain** (reduction of purposeless activity which simply burns calories at the expense of the infant's growth and health)

35

## The Benefits For Kangaroo Care (Cont.)

8. **Decreased crying** – better cerebral blood flow, higher SaO2
9. Longer periods of alertness – more stable physiology
10. Opportunities to **breastfeed** and enjoy the healthful benefits of breast milk (prevents hypoglycemia).
11. Increases initiation-duration-exclusivity – **supports and successful breastfeeding** session – swifter transition to nipple and breastfeeding
12. Possibly less severe Neonatal Abstinence Syndrome (Ludington-Hoe et al., 2015)
13. Earlier **bonding**
14. Fewer infections, **shorter lengths of stay.**

36

## The Benefits For Kangaroo Care (Cont.)

### ♦ For Mothers:

1. Decreases maternal **stress**
2. Minimize maternal **depression** – prevents depression
3. Hastens recovery from birth, **decreases lochia** enhances placental expulsion
4. Lowers maternal BP, help prevention & recovery from postpartum hemorrhage
5. Enhances **maternal sensitivity** and responsiveness **in ability to care** for their babies.
6. Enhances maternal **attachment/ bonding**, feeling of closeness with babies.

37

## Cont.

7. Increases **confidence and competence** in providing infant care.
8. Creates more nurturing interactions.
9. **Increases milk production** and lengthens breastfeeding
10. **Improves interactions** with child for years

38

## The Benefits of Kangaroo Care (Cont.)

❖ **Family :**

1. Economical
2. Better follow-up
3. Promotes bonding among the family members.

❖ **Hospital/institution :**

1. Saves materials like incubators, O2 cylinders
2. Saves in man power in term of nursing staff

❖ **Nation:**

1. Reduces mortality & infant mortality
2. Healthy and intelligent children, adds to the nation's health and wealth.

39

[figure not shown]
- **PHOTOS ON KC PROCEDURE**

40

- **VENDOR Wrap**
- **Sitting Transfer**
- **Standing Transfer**

### Vendor Wrap

## Standing Transfer

[figure not shown]

## Sitting Transfer

Document And Follow-up Policy For  
Kangaroo Care.

44

## Documentation

- The diary for the infant progress on
- KC frequency – 1 hour per day and 4-5 hours per week in the first 3 months old
- KC attainment of breast feeding nearly exclusive
- Weight gain monitored in every 1 month and 3 months old of corrected ages.

45

## Kangaroo Feeding Policy

### ❖ Kangaroo Care Feeding

- Kangaroo position is ideal for breast feeding
- Exclusive breast feeding is the policy
- Feeding is done once in **90 -120 minutes** before KC
- If the baby can suckle, it is promoted
- If baby cannot suckle, express breast milk to be fed.
- If the baby is unable to swallow, EBM is fed by nasogastric tube.

46

## Early Discharge

- Criteria for discharge
- Weight gain at least 1.8kg
- Baby should feed well on breast milk
- Temperature should be maintain
- No evidence of illness

[figure not shown]

48

## Follow - Up

- After discharge, KC is continued at home until the **first 3 months** old
- Follow up is done weekly to ensure the baby feeding well and gaining about 15 – 20g weight daily
- Afterwards once a month till the baby reaches 52 weeks of post conceptional age.

49

So, what's not to like?

Why isn't KC used routinely, consistently and continuously every time mother is there?

50

Showing video on standing transfer

53

Showing video on sitting transfer

51

### LEARNING OUTCOMES

- Define sitting transfer kangaroo care technique.
- State the purpose of sitting transfer of kangaroo care technique.
- Explain the indication and contraindication of sitting transfer kangaroo care technique.

Cont.

---

- Explain the principles of assessment of sitting transfer kangaroo care
- Prepare the infant and mother for sitting transfer kangaroo care
- Demonstrate the sitting transfer correctly and skillfully.

## Definition

### **Sitting Transfer Kangaroo Care :**

- The mother is already sitting in a chair or recliner when the infant is given to her for KC.
- Place the **infant prone on mother chest** from the **incubator** pass to the **mother sitting** on the chair.

### **Purpose of sitting transfer for Kangaroo Care technique**

1. To ensure the proper and **safe positioning** of infant on mother bear chest.
2. To prevent infant from **slipping down** from the mother chest.
3. To ensure mother **support infant's back and buttocks** during Kangaroo Care technique.

## **Indication of sitting transfer Kangaroo Care technique**

---

1. Infant > 28 week of gestational age and > 1500 g
2. Infant clinically stable and eligible for KC
3. Mother post delivery (SVD) or Caesarean)
4. Mother with back pain.
5. Mother with first baby.

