### **1.7.2 Kangaroo care (KC)**

As stated by Ludington-Hoe et al., 2010 & 2018; Charpak & Ruiz-Palaez, 2011, KC is defined as the simple intervention of chest-to-chest, skin-to-skin contact between an infant and a significant mother. The preterm infant's head is turned to one side so that the ear of the infant is above the mother's heart. Wearing only a diaper, the infant is placed in a prone frog-like position (arms and legs flexed), head turned to one side and neck straight (open airway) for a minimum of one hour per session so as to complete one cycle of sleep (active sleep, quiet sleep and return to active sleep), Ludington-Hoe et al., 2018.

In this study, KC refers to a special holding technique where the premature infant is held in a vertical upright position. The premature infant wears only a diaper or a head cap/booties (optional for infants with a body weight <1500grams) and is placed on the mother's bare chest (between the mother's breasts). The infant's head is turned sideways facing either right or left, both knees and elbows are bent (M position) to form a frog-like posture. The premature infant's head and torso are covered from its feet until the auricular lobule (earlobe) with either the mother's clothes, a tube or a small blanket to retain warmth in order to promote the infant's growth and development.

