### **2.3.5 Premature Infant**

A premature infant is one born before 37 complete weeks, according to Phillips, Goldstein, Hougland (2013). Furthermore, the classification of prematurities such as mild, moderate, and severe is based on gestation as follows, according to About Kids Health (2016):

- i) Mild prematurity applies to an infant born within 33 to 36 weeks of gestation, and/or is approximately 1500 and 2500 grams in birth weight.

- ii) Moderate prematurity relates to an infant born between 28 and 32 weeks of gestation, with a birth weight ranging from 1000 to 1500 grams.
- iii) Extreme prematurity refers to an infant born before 28 complete weeks of gestational or with a birth weight of less than 1000 grams

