#### **3.7.1 Inclusion and exclusion criteria**

The decision to perform kangaroo care (KC) does not rely solely on the degree of neurodevelopment or postpartum age, but also on the stability of the infants. After birth, or within a few hours, days, or weeks, the baby can still be in an incubator or cradle as well as be clinically stable.

The selection of infants was based on the following criteria:

- premature infant at corrected age between 28 weeks to 36+6 weeks' gestation.
- infant clinically stable, eligible for KC, and admitted to the NICU.

The exclusion criteria for infants were:

- surgical infant i.e cleft lip, cleft palate, spina bifida, exomphalos and omphalocele.
- infant required medical treatment eg. prolonged phototherapy treatment.
- trisomy 21.

Mothers with preterm infants in the NICU who were able to perform the KC technique.

Therefore, the selection criteria for mothers were as follows:

- all mother-premature infants with corrected age between 28 to 36+6 weeks of gestation.
- mothers who were older than 18 years old and were able to give their consent.
- mothers who could speak and read either English or Malay.
- mother had no medical or surgical condition which required medication which interfered with breastfeeding and was eligible to perform KC for her preterm infant.

The exclusion criteria for mothers were:

- mothers who had previous premature infants.
- mother of quadruplets or more
- mother who had any medical and surgical conditions that required medication which interfered with breastfeeding and was not eligible to perform KC for her premature infant

Nurses also play a significant role in caring for mothers and babies during the maternal, perinatal and postnatal phases. They need to have expertise and confidence in their skills to provide neonatal treatment. The target group of nurses was registered nurses employed in UMMC's NICU. They were all invited to participate in this analysis to ensure the sample size was sufficient.

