### 2.2 Mother

- Chair
- Blouse open in front
- Small mirror

3. Demonstrate and return-demonstrate

[figure not shown]

Figure 3.1: Shows the kangaroo care position

a) Greet mother, introduce yourself, and explain the purpose of the procedure.

Rational(R): Mother understands the correct KC position for the infant;(head midline, well flexed, nares/mouth visible)

b) Prepare the mother's and infant's equipment & screen mother and infant for

privacy.

R: Mother is comfortable and able to sit for a minimum of 60 minutes per day.

The mother should remove the bra and wear a blouse or robe that opens in front or tube. The mother eliminates the need to disrupt the KC session bowels opened (BO) and passed urine (PU).

c) Position the KC chair at the side of the incubator door.

R: To prevent unnecessary tension on the lines during transfer.

d) Assist the mother to sit on the chair next to the incubator with her blouse/shirt open or robe.

R: Ready to receive the infant for KC and ensure the entire body over the naked chest and abdomen is covered.

e) Monitor infant vital signs, such as temperature, respiration and heart rate; 15-30 minutes before and after KC.

R: To monitor baseline temperature, respiration and heart rate.

f) Place the infant in the supine position with receiving napkin/blanket underneath the head and torso / back of the infant.

R: To avoid heat loss.

g) Take off the infant's clothes and dress the infant in a diaper and head cap only.

R: To check if BO or PU and prepare for KC.

h) Cover the ends of the blanket to cover arms, legs, intravenous (IV) lines, and lead wires around the infant.

R: To prevent heat loss and dislodging all the lines.

i) Pick up the infant with the hand under head and buttocks close to your chest.

R: To support and stabilize the infant during transfer.

j) Place the infant prone on the chest of the mother, and pull the ends of the blanket

over.

R: To assure proper chest-to-chest; skin to skin contact.

k) Assure proper, safe positioning of the infant; head midline, neck straight, nares and mouth visible, arms and legs in a bent position.

R: To get the advantages of the KC effect.

l) Instruct mother to fold her arm across infant's back (non-dominant hand) and buttocks (dominant hand)

R: To prevent slipping down from her chest.

m) Place an additional folded blanket or wrap across the infant's back. Advise mother to cover her body or wear the blouse open in front (button) on top of the premature infant.

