## Contraindication For Kangaroo Care

### ❖ Infants.....

1. Wt <1000 g & < 28 week GA
2. Under radiant warmer – still quite sick
3. Umbilical artery catheter (UAC & UVC) - blocked
4. Chest tubes – dislodged during KC.
5. TPN – percutaneous line place in the arm- dislodged.
6. Scalp vein lvs, IVH grade 3 & 4 (bleeding into the brain) – too sick to participate in KC
7. Nil by mouth – may try to go to the breast during KC

23

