## **Contraindication of sitting transfer Kangaroo Care technique**

---

1. Infant < 28 week of gestational age and < 1500 g
2. Post caesarean mother.

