## Indication of standing transfer Kangaroo Care

---

1. Infant > 28 week of gestational age and > 1000 g
2. Infant clinically stable and eligible for KC
3. Mother confidence and ready for KC her infant.

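### Entry sets no weight limit and leaves KC eligibility undefined, while the training material's weight and caesarean conditions conflict, so some enrolled infants have no consistent handling instruction

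*Combined protocol and SAP*

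**What the plan says.** **Entry.** The first infant criterion in section 3.7.1 is "premature infant at corrected age between 28 weeks to 36+6 weeks" of gestation. The second requires the infant to be clinically stable, eligible for KC and admitted to the NICU. Neither list of infant criteria contains a weight, and eligibility for KC is not defined there.

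**KC definition.** Section 1.7.2 makes the head cap and booties "optional for infants with a body weight <1500grams", so it contemplates KC at those weights.

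**General slides (Appendix P).** The indication slide lists overlapping bands: above 1,000 to 1,500 g; birth weight 1,300 to 1,800 g after 7 days; and above 1,500 g combined with clinical stability. The contraindication slide begins with "Wt <1000 g & < 28 week GA".

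**Sitting-transfer slides.** The indication is "Infant > 28 week of gestational age and > 1500 g" and the contraindication is "Infant < 28 week of gestational age and < 1500 g". Caesarean delivery is on both lists.

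**Standing-transfer slides.** The indication is "Infant > 28 week of gestational age and > 1000 g". The contraindication has the same form as for sitting, with 1000 g as the weight, and lists post-caesarean mothers.

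**Written steps for mothers (section 3.11, practical session).** Step d reads "Assist the mother to sit on the chair next to the incubator with her blouse/shirt open or robe", and the infant is then placed on her chest. No step carries a weight condition.

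**The concern.** A nurse or mother who turns to different pages finds different conditions for handling the same small infant. Those at or below 1500 g are affected most, because the sitting indication excludes them while the mothers' written procedure is seated. This bears on infant safety and on whether the intervention is delivered uniformly.

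There is also a design question. Section 3.16 places control data collection in February to July 2018, nurse training in August and September 2018, and the experimental group from October 2018. The slide limits entered the unit's teaching only between the two recruitment periods. If they came to be used as the meaning of eligible for KC, light infants could be kept out of the experimental group but not the control group. Length of stay is a primary outcome (section 3.9), and discharge depends on reaching a predetermined weight (section 3.16.4), so a one-sided filter on weight would matter.

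**Working it through.** No sample size, power or error-rate figure is involved. The check takes the stated conditions literally and applies them to example infants who meet the corrected-age criterion and are assumed clinically stable.

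**Conditions used**
- Entry: corrected age 28 to 36+6 weeks, no weight limit (section 3.7.1).
- Sitting indicated: age > 28 weeks and weight > 1500 g.
- Standing indicated: age > 28 weeks and weight > 1000 g.
- Contraindications: age < 28 weeks and weight < 1500 g (sitting) or < 1000 g (standing; the general slide uses the same pair).

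| Infant | Within entry range | Sitting indicated | Standing indicated | Contraindicated, read literally |
|---|---|---|---|---|
| 30 weeks, 900 g | yes | no (900 < 1500) | no (900 < 1000) | no (30 is not < 28) |
| 30 weeks, 1200 g | yes | no (1200 < 1500) | yes (1200 > 1000) | no |
| 30 weeks, 1600 g | yes | yes | yes | no |
| exactly 28 weeks, any weight | yes | no (28 is not > 28) | no | no |

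**The contraindications.** Each joins weight to an age below 28 weeks. Entry starts at 28 weeks, so read literally none of them ever bars an enrolled infant on weight. If the joining word is meant as *or*, the 900 g infant is contraindicated for KC although entry would admit it, and the 1200 g infant is contraindicated for the sitting transfer that the mothers' written steps use. Neither reading makes the documents agree.

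**Adding mode of delivery.** Mothers delivered by caesarean are not excluded by section 3.7.1, and delivery type is recorded (section 3.8.1). For them:
- sitting is both indicated and contraindicated, at any infant weight;
- standing is contraindicated, at any infant weight.

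So a 1200 g, 30-week infant of a caesarean mother does not meet the weight indication for sitting, and the standing transfer, open to it on weight, is barred by delivery type.

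**The case against.** Several points on the other side are sound.

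- Two techniques may properly have two weight limits. From above 1000 g to 1500 g the general slide lists KC as indicated and the standing transfer is open, so the sitting limit is not a bar on KC. This stands. The conflict remains because the written steps for mothers are seated without a limit, and because of the caesarean lines.
- Mothers are not taught sitting alone. Section 3.16.2 describes videos of both transfers, and Appendix M(a), item 4.6, has both demonstrated. This softens the clash but does not supply a rule for choosing between them.
- The researcher screened and selected both groups (sections 3.16.1 and 3.16.2) under the same requirement of stability and eligibility. Section 3.16.4 adds tolerance of enteral feeds and matching by corrected age. Nothing says the slide weights were used at recruitment, so one-sided filtering is only a possibility.

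A reader might go further in three ways that the documents do not support.

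- That entry rests on corrected age alone: stability and eligibility are also required; what is missing is a weight and a definition.
- That about half the sample is affected, because section 2.3.5 describes infants "born between 28 and 32 weeks of gestation, with a birth weight ranging from 1000 to 1500 grams". That counts weeks of the entry range, not infants. It is a cited general classification of birth weight by gestation at birth, whereas entry uses corrected age, and the documents give no distribution of enrolled infants by weight.
- That the bias in length of stay can be sized from the stays of 36 to 11 days cited in section 1.2 for 32 to 36 weeks. Those are outside figures that do not cover 28 to 32 weeks, and no filtered fraction is known.

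**Conclusion.** The inconsistency is real and rests only on the text. Entry has no weight limit and no definition of KC eligibility; the weight conditions differ between the KC definition, the general slides, the two transfer slides and the mothers' steps; and the caesarean lines contradict each other. Some infants who can be enrolled therefore have no consistent handling instruction. How many cannot be stated.

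The possible effect on group comparability assumes that the slide limits were used to judge eligibility in the experimental phase. The plan neither says so nor prevents it, and section 3.19.1 names no weight covariate in its covariance analysis. No size can be given for any effect on length of stay. The point deserves correction because it concerns the handling of the smallest infants, but it does not show that the primary comparison is biased.

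**What to change.** The clinical team should reconcile sections 1.7.2, 3.7.1 and 3.11 (practical steps), the indication and contraindication slides in Appendix P, and the sitting- and standing-transfer slides into one consistent rule. It should cover weight, the joining of weight with age, infants of exactly 28 weeks, and caesarean delivery. No threshold or preferred transfer is proposed here.

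Then:
- state the rule in the entry criteria, where it defines eligibility for KC, and repeat it unchanged in the mothers' and nurses' procedures;
- apply the same rule to both groups' data sets, including control infants already recruited;
- record the transfer type beside the weight at KC initiation, which section 3.9 already collects; recruitment weight (section 3.16.4) can serve for control infants who had no KC.

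The cost is protocol and slide wording plus one added data item. Some light infants in either group may fall outside the reconciled rule; their number should be reported by group.
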